# 4.4 Study stopping rules

**4.4.1** Study enrollment continuation with expedited review by the DSMB will occur for a threshold incidence of biopsy proven acute rejection of 10% on a rolling basis consistent with the following number of subjects with the event of rejection per enrolled patients (modified Simon's two-stage design strategy for 75-85% probability):

Number of subjects with Rejection (n)	Number of subjects enrolled in Q8 group
2	14
4	41
7	83

**4.4.2** Study enrollment suspension pending expedited review by the DSMB will occur for a threshold incidence of biopsy proven acute rejection of 20% on a rolling basis consistent with the following number of subjects with the event of rejection per enrolled patients (modified Simon's two-stage design strategy for 75-90% probability):

Number of subjects with Rejection (n)	Number of subjects enrolled in Q8 group
3	14
5	35
15	83

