# 6.8 Data Safety Monitoring Board (DSMB)

A Data Safety Monitoring Board will be established to monitor the safety of the patients during this trial. The initial meeting of the DSMB will occur prior to the start of the study in which study start will be defined as the date on which the first patient enrolled in the study. Subsequent meetings will occur three months from study start and then every six months thereafter. The DSMB will be composed of 3 official members who are members of the Transplant Nephrology, Transplant Surgery, or the Nephrology community. DSMB members must be independent of this study and may not serve as investigators or participate in the care of subjects enrolled in this study. See Appendix 2 for DSMB membership and Appendix 3 for DSMB charter.

DSMB recommendations to modify or prematurely terminate the study shall require a unanimous vote of all voting DSMB members.

To reduce the risk of disclosure of study information to non-DSMB members, board members shall not copy, disseminate, communicate, or allow access to information pertaining to this study. Any copies of materials prepared for distribution to DSMB members will be clearly labeled as confidential. All materials will be identified only with subjects' unique study identification number and personal information that could lead to the identification of the study subject will not be made available to the DSMB membership. All communications and confidential study data will be stored in a secured area by DSMB members.

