# 7. Study design and methods

After randomization into either the q-1M or q-2M dosing groups, belatacept will be administered at a dose of 5 mg/kg, the same dose the patient was taking at the beginning of the study. The visit window for the q1M group will be per standard of care and the visit window for the q2M group will be +/- 5 days. See the attached dosing schedule and budget for the schedule of drug administration and lab tests. Q-2M patients will have lab tests every two weeks starting at week 4 of the study (the first time point when the q-1M patients receive belatacept and theq-2M patients do not). The q-2M group will have labs performed every two weeks from week 4 through week 16. With the exception of every two week labs for the q-2M group from week 4 through week 16 and frequency of belatacept administration, both groups of patients will be treated the same in all ways. Labs will be monthly otherwise. For study purposes, patients will receive a chemistry profile at every lab draw and antibody assessment (PRA/DSA) labs at enrollment, and 6 and 12 months. Otherwise they will be managed per standard of care as clinically indicated. For mechanistic studies, blood and serum will be drawn and stored on select study patients.

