# 8. Study Population

The trial population consists of adults ≥18 years of age who are first-time transplant recipients of either living donor or deceased donor renal transplants. Patients of all races and ethnicities will be included.

This is an intention to treat, randomized, controlled trial. There will be a total of 166 subjects, randomized in equal numbers, 83 patients in each arm. We anticipate needing to consent/enroll 200 patients to achieve 166 randomized subjects accounting for an approximate 15% screen failure rate. All patients will be actively followed in the study for 12 months following enrollment. The study is projected to last 2 years.

Before any study procedures are performed, the details of the study will be described to subjects, and they will be given a written informed consent document to read. Patients who consent to participate in the study will sign and date the informed consent document in the presence of study personnel. Only patients who have given informed written consent will be included in this study.

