The mean eGFR at one year post-transplant for patients receiving belatacept at the Emory Transplant Center has been found to be 60.2 ml/min/1.73 m² with a standard deviation of 14.5 ml/min/1.73 m². When patients with an eGFR less than or equal to 35 ml/min/1.73 m² are excluded, the mean eGFR at one year post-transplant has been found to be 61.5 ml/min/1.73 m² with a standard deviation of 13.1 ml/min/1.73 m². Based on this inclusion criterion, the table below details several scenarios of potential sample size for different equivalence margins in order to attain 80% power for a significance level (alpha) of 0.05.

Calculated GFR is a continuous variable and will be assessed at monthly intervals (increasing to every two weeks from week 4 to 16 in the q-2M group) throughout the study. The secondary time points of rejection, death, graft lost, and HLA antibody production will be assessed at 6 and 12 months. Total cost, clinic visits, hospitalizations, biopsies and patient satisfaction will be assessed at 12 months.

Assuming a standard deviation of 13.1 ml/min/1.73 m^2:

Equivalence margin	N per group	Sample Size (total
(ml/min/1.73 m  )		N)
5.0	119	238
5.5	98	196
6.0	83	166
6.5	71	122
7.0	61	122

For example, assuming the standard deviation for eGFR at one year post-transplant is 13.1 ml/min/1.73 m^2, 166 patients total (83 per treatment group) are required to be 80% sure that a

two-sided 95% confidence interval will exclude a difference in mean eGFR between the treatment groups of more than 6.0 ml/min/1.73 m^2.

This study also aims to compare the secondary outcome of acute rejection rate between the q-1M and q-2M dosing interval groups. The one-year post-transplant acute rejection rate among patients treated with belatacept is expected to be 1-2%; based on this assumption, the table below details several scenarios of potential sample size for absolute differences in acute rejection rate in order to attain 80% power for a significance level of 0.05.

AR rate for reference group	AR rate for intervention group	Absolute difference	N per group	Sample Size
(q-4)	(q-8)	difference		(total N)
1%	4%	3%	137	274
1%	5%	4%	77	154
1%	6%	5%	49	98
1%	8%	7%	25	50
2%	5%	3%	270	540
2%	7%	5%	97	194
2%	8%	6%	68	136
2%	9%	7%	50	100

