## **Stopping Rules**

The study as a whole may be stopped by the Investigator and DSMB if there are reasons for which continuation of study is no longer justified, such as:

- Unacceptable delay of study completion,
- Low recruitment rate,
- A large number of study participants with premature termination,
- Changed benefit-risk ratio according to the efficacy and/or safety results from this or parallel studies

Study enrollment suspended pending expedited review by the DSMB when:

• 5 of 10 patients in treatment arm (every 2-Month Belatacept infusion) experience acute rejection

Study enrollment continuation with expedited review by the DSMB when:

• 3 of 5 patients in treatment arm (every 2-Month Belatacept infusion) experience acute rejection

In case of premature termination of the entire study, the PI will ensure that IRB/ appropriate Regulatory Authorities are notified within 15 days.

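### The protocol and the DSMB charter set contradictory rejection triggers for the q-2M arm, and no text says which governs

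*Combined protocol and SAP*

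**What the plan says.** Section 4.4 of the protocol has two tiers, both counting biopsy-proven acute rejection in the q-2M (Q8) group. In 4.4.1 (10% threshold), enrollment continues with expedited DSMB review at 2/14, 4/41 or 7/83. In 4.4.2 (20% threshold), the action is stronger: "Study enrollment suspension pending expedited review by the DSMB will occur for a threshold incidence of biopsy proven acute rejection of 20"%, at 3/14, 5/35 or 15/83. Both tiers apply "on a rolling basis consistent with the following number of subjects with the event of rejection per enrolled patients".

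The DSMB charter, under Stopping Rules, uses the same two actions with other numbers. Enrollment is suspended pending expedited review when "5 of 10 patients in treatment arm (every 2-Month Belatacept infusion) experience acute rejection". It continues with expedited review when "3 of 5 patients in treatment arm (every 2-Month Belatacept infusion) experience acute rejection". The charter does not refer to section 4.4, and section 4.4 does not refer to the charter.

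On arm size, section 8 states: "There will be a total of 166 subjects, randomized in equal numbers, 83 patients in each arm". On the expected event rate, section 10 states: "The one-year post-transplant acute rejection rate among patients treated with belatacept is expected to be 1-2"%.

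**The concern.** Acute rejection is a main safety concern of the longer dosing interval. The suspension trigger is the one numeric device that halts further exposure at group level. Two versions of it exist, with the same actions at different counts. The DSMB works from its charter, which is meant to set the criteria for its recommendations, while the investigators work from the protocol. An early cluster of rejections could therefore suspend enrollment under one text and leave it open under the other, and the dispute would have to be settled with unfavorable data already in hand.

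The charter is also odd on its own terms. Its milder action needs a higher observed rate (3/5 = 60%) than its stronger one (5/10 = 50%). It counts acute rejection without saying whether biopsy proof is needed. Section 10 mentions both clinically suspected and biopsy-proven rejection, so the two texts could be applied to different counts.

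**Working it through.** **Plan's own figure.** Section 4.4.2 attaches a probability of 75-90% to its rows without defining it. With X ~ Binomial(n, 0.20), P(X ≥ r) is 55.2% for 3/14, 85.7% for 5/35 and 71.1% for 15/83. The cumulative chance of having crossed by each row is 55.2%, 87.3% and about 91%. The stated range is therefore not reproduced row by row, and the overall figure lies just above its upper end. The conflict does not depend on this.

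**The two texts side by side, for the same q-2M data:**

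| Rejections in q-2M | Protocol 4.4 (rolling) | Charter |
|---|---|---|
| 2 of first 5 | expedited review, enrollment continues (2 within 14) | no trigger |
| 3 of first 5 | suspend enrollment (3 within 14) | expedited review, enrollment continues |
| 3 or 4 of first 10 | suspend enrollment | no suspension |
| 5 of first 10 | suspend enrollment | suspend enrollment |

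Reading the 4.4.2 rows as fixed checkpoints at 14, 35 and 83 does not remove the difference. Three rejections among the first 5 are still at least 3 among 14 when the 14th patient enters. The levels remain 3/14 = 21% against 5/10 = 50%.

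**How often the rules diverge, with every counted patient followed for 12 months.** Inputs are the printed counts and assumed true rates: 20% and 10% are the plan's own thresholds, and 2% is the top of its expected range.

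| True rate | P(≥3 of 14) | P(≥5 of 10) | P(3 or 4 of 10) | P(≥3 of 5) |
|---|---|---|---|---|
| 20% | 55.2% | 3.3% | 28.9% | 5.8% |
| 10% | 15.8% | 0.2% | 6.9% | 0.9% |
| 2% | 0.25% | <0.001% | 0.09% | 0.008% |

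Example at 20%: P(≥3 of 5) = 10(0.2³)(0.8²) + 5(0.2⁴)(0.8) + 0.2⁵ = 0.0512 + 0.0064 + 0.0003 = 0.058.

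**The same count during accrual.** Section 4.4 divides by subjects enrolled, so early patients have short follow-up. Take 6 q-2M entries per month (section 1) and a 20% 12-month rate. The 15th patient then enters at 15/6 = 2.5 months. By simulation, the chance of 3 rejections before that entry is about 0.3% with constant hazard, 10% if all rejections fall within 3 months of entry, 2% if within 6 months, and 0% if they fall in months 3-12. The full-follow-up figures are therefore upper values, and timing decides how far below them the trial would sit.

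**The 15/83 row.** The q-2M arm is 83, so at this row no q-2M enrollment is left to suspend and the expedited review is the only working part. At every number enrolled, the 4.4.1 count is below the 4.4.2 count (2 against 3, then 4 against 5, then 4 or 7 against 15). Review under 4.4.1 is therefore always triggered first.

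**The case against.** The best defense is that a trial can obey both texts by applying the stricter one. The charter's continuation at 3 of 5 could be read as permission, the 55% against 3% comparison would then show only that the charter is looser, and all of it matters only at rates far above the expected 1-2%. The point about rates stands: at 2% the literal clash is negligible. But no text tells anyone to apply the stricter rule, and a boundary exists for the case where the arm does much worse than expected. If the charter counts clinically suspected rejections too, its total rises faster, but 3 biopsy-proven rejections in 5 still produce opposite actions.

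A reader might also infer that q-2M patients are left without group-level protection once enrollment closes, because 4.4.2 acts only on enrollment. At a 20% rate, simulation does put the first 4.4.2 crossing after the 83rd entry in 60-63% of trials with constant hazard and 70-71% with rejections in months 3-12 (4-9% if all fall within 3 months). The documents do not support that inference:

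- Section 6.9 runs DSMB reviews until the last subject completes follow-up.
- The charter has the board advise continuing, modifying or discontinuing, including for a subgroup, at each meeting, and allows ad hoc review within 4 days of a request.
- Section 6.3 returns individual patients to q-1M after grade 1B or greater or antibody-mediated rejection.
- On early surveillance, section 7 states: "The q-2M group will have labs performed every two weeks from week 4 through week 16".
- Review under 4.4.1 comes first. A late 4.4.2 crossing with no 4.4.1 trigger while enrollment was open occurs in about 3% of trials with constant hazard, essentially none in the early-rejection cases, and 16% with months 3-12.

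It is true that "DSMB recommendations to modify or prematurely terminate the study shall require a unanimous vote of all voting DSMB members", but that governs what follows a review, not whether one takes place. Preferring a numeric rule for treated patients over DSMB judgement is a design preference, not an error in the plan.

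**Conclusion.** The contradiction is real and can be seen from the text alone. The protocol and the charter assign different actions to the same rejection counts in the q-2M arm, define the counted event differently, and give no order of precedence. It should be fixed.

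Its practical size is modest. At a true 20% rate with full follow-up, the protocol's first suspension trigger is far more likely to be met than the charter's (55% against 3%), and the outright opposite instruction at 3 of 5 has probability 5.8%. These figures assume independent patients with 12 complete months each. During accrual they fall by an amount that depends on rejection timing, which the documents do not give. They should not be read as the chance that this trial takes a wrong decision.

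The 15/83 row merits a clarification at most.

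**What to change.** **Main change.** In the charter's Stopping Rules, replace both numeric rejection triggers (3 of 5 and 5 of 10) with: *Rejection triggers are those in protocol sections 4.4.1 and 4.4.2 (biopsy-proven acute rejection).* This settles precedence, thresholds and event definition together. The rows in 4.4, the sample size and the DSMB's discretion stay as they are.

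**Optional clarification.** In 4.4.2, state that counting runs to the last q-2M patient's month 12 and that, once enrollment is complete, the expedited review records whether q-2M patients continue or return to q-1M. This makes existing duties explicit and adds no new rule.

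**Cost.** A wording amendment to the charter and, if wanted, one sentence in the protocol. The lower thresholds add little burden if the arm behaves as expected: at a true 2% rate, any 4.4.2 row is crossed in about 0.3% of trials with full follow-up, and reviews can be held by teleconference.

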### 5.0 Investigational Drug Supplies

All medications will be obtained from commercial pharmacies and billed to the subject's insurance provider. Therefore investigational drug services will not be utilized.

#### 6.0 Safety Issues

Adverse events will be monitored and documented for the duration of the study and for 30 days after study completion.

# 6.1 Women of Childbearing Potential (WOCBP)

Pregnant or nursing (lactating) women, where pregnancy is defined as the state of a female after conception and until the termination of gestation. A spot urine pregnancy test will be performed only on WOCBP after the patient is enrolled in the study. If the spot urine pregnancy test is positive, it will be, confirmed by a serum human chorionic gonadotrophin laboratory test. A positive serum pregnancy test (>5 mIU/mL) will exclude a female patient from participation in this study.

Women of child-bearing potential, defined as all women physiologically capable of becoming pregnant, including women whose career, lifestyle, or sexual orientation precludes intercourse with a male partner and women whose partners have been sterilized by vasectomy or other means must agree to use birth control throughout their participation in the study.

If a subject becomes pregnant while receiving belatacept this event will be reported in accordance with SAE reporting.

If a WOCBP indicates plans to pursue pregnancy, or reports an unanticipated pregnancy, the subject will be withdrawn from further participation in the study, but followed for safety and pregnancy outcome.

#### **6.2 Clinical Adverse Events**

Because Belatacept is an FDA approved medication and we only propose to decrease the dosing frequency from every 1months to every 2 months, only the clinical adverse events of worsening kidney function, graft loss, kidney transplant rejection, increased donor-specific antibody formation, infection, and cancer will be assessed and recorded unless the event meets the definition of a serious adverse event. We will also record any adverse events that may occur as a result of blood draws specifically done for the study.

# 6.3 Rejection

The occurrence of rejection requires special consideration:

- In the standard of care q-1M dosing group, any grade of rejection will be treated in accordance to our established ETC protocol for the treatment of rejection (Appendix 1).
- In the treatment arm, q-2M dosing group, any grade of rejection will be treated in accordance to our established ETC protocol for the treatment of rejection (Appendix 1).
   However, depending on the grade of rejection, study subjects will either remain in the q-2M treatment group or be converted over to the standard of care q 1M group.
  - If the rejection is graded as borderline or 1A: the patient will remain in the q-2M treatment arm with close follow up and surveillance consistent with routine practice.
  - If the rejection grade is 1B or greater, then the patient will be converted back to q-1M standard of care dosing but will remain in the study.
  - If the rejection is antibody mediated rejection (AMR), then the patient will be converted back to q-1M standard of care dosing but will remain in the study.

Rejection Grade	Gro	oup
	Q-1M	Q-2M
Borderline or 1A	Remain inQ-1M	Remain in Q-2M
1B or Greater	Remain in Q-1M	Convert to Q-1M
AMR	Remain in Q-1M	Convert to Q-1M

### 6.4 Severity

Severity of the adverse event will be defined as follows:

Mild – Discomfort noticed but no disruption of normal daily activity

Moderate – Discomfort sufficient to reduce or affect daily activity

Severe – Inability to work or perform normal daily activity

Life Threatening – Represents an immediate threat to life.

### 6.5 Determination of Relationship of Adverse Event to Belatacept Dosing

There will be three categories of possible relationship between the adverse event and belatacept dosing. Determination of drug-relatedness of the adverse event to belatacept dosing will be determined by the investigator.

# Possible (must have first two)

A possible relationship will be assigned to an adverse event when the connection with belatacept administration appears unlikely but cannot be ruled out with certainty. An adverse event will be considered possible if:

- 1. It follows a reasonable temporal sequence from administration of belatacept
- 2. It cannot be reasonably explained by the subject's clinical state, environmental or toxic factors, or other modes of therapy administered to the subject
- 3. It follows a known pattern of response to belatacept

### **Remote** (must have first two)

An adverse event will be considered remote if:

- 1. It does not follow a reasonable temporal sequence from administration of belatacept
- 2. It may readily have been produced by the subject's clinical state, environmental or toxic factors, or other modes of therapy administered to the subject.
- 3. It does not follow a known pattern of response to belatacept.
- 4. It does not reappear or worsen when belatacept is re-administered.

# Unrelated

An adverse event will be considered unrelated if it is judged to be clearly and incontrovertibly due only to extraneous causes such as disease, environment, etc. while not meeting the criteria for drug relationship as listed above for remote, possible, or probable.

#### 6.6 Serious Adverse Event

A serious adverse event is any experience that suggests a significant hazard, contraindication, side effect or precaution and meets at least one of the following criteria:

- Is fatal (results in death);
- Is life-threatening;
- Requires in-patient hospitalization or prolongs existing hospitalization;
- Results in persistent or significant disability/incapacity;

- Results in a congenital anomaly/birth defect;
- Is medically significant or requires intervention to prevent one or other of the outcomes listed above.

The clinical judgment of the investigator shall be used in deciding whether a certain situation may warrant consideration as a serious adverse event but may not meet the above criteria. This medical event may not be immediately life-threatening or result in death or hospitalization but may jeopardize the subject or may require intervention to prevent one of the outcomes listed in the definitions above.

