# 3.3 Safety

Patient safety will be assessed by monitoring the incidence of serious adverse events, infections, malignancies, morbidity, renal function, and rejection.

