# 4. Safety Assessments

#### 4.1 Adverse Events

During the study, safety assessments will include:

- Incidence of adverse events, serious adverse events, malignancies, opportunistic infections, and premature withdrawal due to adverse events
- · Patient and Graft loss
- Changes in immunosuppressive regimen

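### Section 6.6 makes serious adverse event status depend on a hazard judgement as well as on outcome, so a serious outcome seen as incidental can lose SAE reporting and, if unlisted in 6.2, any adverse-event record

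*Combined protocol and SAP*

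**What the plan says.** Section 6.6 opens by defining an SAE as "any experience that suggests a significant hazard, contraindication, side effect or precaution and meets at least one of the following" criteria. Six criteria follow under that lead-in, among them "Is fatal (results in death") and "Requires in-patient hospitalization or prolongs existing hospitalization". A closing paragraph adds discretion: "The clinical judgment of the investigator shall be used in deciding whether a certain situation may warrant consideration as a serious adverse event", for situations that may fall outside the criteria.

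Other sections rely on this definition:

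- **6.2** limits adverse-event collection to six types (declining kidney function, graft loss, rejection, rising donor-specific antibody, infection, cancer). The rule ends: "infection, and cancer will be assessed and recorded unless the event meets the definition of a serious adverse event". Events caused by study blood draws are also recorded.
- **6.7** sends serious, unexpected events to the DSMB within 7 days. They go to the IRB within 10 business days only if also unanticipated and belatacept-related.
- **Section 10** (last paragraph) says the board is told of every SAE, and the **DSMB charter** (Scheduled meetings) supplies SAE narratives.
- **3.3** names SAEs first among the safety measures: "Patient safety will be assessed by monitoring the incidence of serious adverse events, infections, malignancies, morbidity, renal function, and rejection".
- **6.0** extends adverse-event documentation to 30 days after study completion.

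Causality has its own step in **6.5**, with the categories possible, remote and unrelated.

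**The concern.** Seriousness is normally a matter of outcome, and causality is judged afterwards. Here a condition that reads like a judgement of relevance sits in front of all six outcome criteria. An event can meet a criterion and still not be an SAE because someone considered it incidental.

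That matters more in this trial than it would where all adverse events are collected. Section 6.2 uses the SAE definition as the only route by which an event outside its short list is recorded. The DSMB's expedited report and narratives use the same definition. A narrow reading of the lead-in therefore reduces what the board sees and what can be tabulated at the end.

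**Working it through.** The point concerns the wording of a definition. The plan gives no figure for it, so there is nothing to reproduce or recompute. The check is to read the sections together and trace what happens to an event.

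**Step 1: the logic of 6.6.** SAE = (suggests a hazard, contraindication, side effect or precaution) AND (at least one of six outcome criteria). All six criteria, including death and hospitalization, are subject to the first condition.

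**Step 2: does the closing paragraph repair this?** It lets the investigator consider situations that may miss the criteria. It widens the category by discretion. It does not state that an event meeting an outcome criterion counts even if it fails the first condition.

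**Step 3: is the first condition needed to handle relatedness?** No. Section 6.5 assesses relatedness separately. Section 6.7 applies it only to the IRB line; the DSMB line has no such condition. A hazard test inside 6.6 therefore sits upstream of a DSMB route that was written without one.

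**Step 4: trace an event that meets an outcome criterion but is judged not to suggest a hazard.**

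| Event | AE/SAE record | Other capture in the plan | What is lost |
|---|---|---|---|
| One of the six types in 6.2 | Yes, under 6.2 | Endpoints where applicable | SAE status, 7-day DSMB report if unexpected, SAE narrative |
| Unlisted death within 12 months | None | Secondary outcome (2.2, 3.2), Kaplan-Meier analysis (10), patient loss (4.1) | SAE status, DSMB report if unexpected, cause and narrative |
| Unlisted admission within 12 months | None | Counted per patient and compared by arm (2.2, 3.2, 10) | SAE status, DSMB report if unexpected, cause and narrative |
| Unlisted life-threatening or disabling event, no admission | None | No endpoint; seen only indirectly if it changes immunosuppression (4.1) | In general, the whole event |
| Unlisted death or admission in the 30 days after study completion | None | The 6- and 12-month endpoints do not reach this period | The whole event |

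**Step 5: who applies the condition, and do they know the arm?** Neither is stated. The investigator is implied, because 6.5 and the last paragraph of 6.6 assign judgement there. Knowledge of the arm is inferred from section 7 and the schedule of events: the infusion and laboratory schedules differ visibly and no sham infusion is described.

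**The case against.** The strongest reply is that the lead-in is loose wording and not an operating filter. It names neither belatacept nor relatedness. The relatedness qualifier for the IRB in 6.7 would be largely redundant if 6.6 had already removed unrelated events, and the only judgement that 6.6 gives the investigator widens the category. This is a fair account of what was probably intended. It does not change what the sentence says, and it supports the fix: if seriousness and relatedness are meant to be separate, the clause has no purpose.

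Four stronger conclusions that a reader might draw are not supported:

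- *Deaths and hospitalizations go unrecorded.* Within 12 months both are secondary outcomes with no hazard condition. What can be lost is their SAE status, cause and narrative.
- *The DSMB learns of such events only as SAEs.* It also receives outcome data (section 10), monitors interim safety data, gets updates on matters affecting subject safety, and its chair may ask for further reviews (charter).
- *The clause biases a comparison of SAEs between arms.* Section 10 plans no between-arm SAE test, and the numerical stopping rules use rejection. Different application by arm is possible if the assessor knows the arm, but the documents show neither a direction nor a size.
- *The measures in 4.1 cannot be produced.* Section 4.1 lists "Incidence of adverse events, serious adverse events, malignancies, opportunistic infections, and premature withdrawal due to adverse events". Limited collection is a deliberate choice for which 6.2 gives a reason: an approved drug given less often. The 4.1 measures can be read as covering the events that are collected. That leaves a point to clarify, not a failure of the plan.

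**Conclusion.** The point holds in limited form. As written, 6.6 can deny SAE status to an event that meets an outcome criterion. The event then leaves SAE incidence, the 7-day DSMB report if it was unexpected, and the SAE narratives. If it is also outside the 6.2 list and not a study blood-draw event, it has no adverse-event record at all. The recording gap is mainly in three places: unlisted life-threatening or disabling events, the cause and narrative of unlisted admissions, and the 30 days after study completion.

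No number can be attached. The documents give neither an event rate nor the share of events that would be judged incidental. The primary analysis, sample size and numerical stopping boundaries are unaffected. The conclusion assumes a literal reading of *and*. The inference that an investigator who knows the arm applies the clause bears on possible bias, and the gap itself does not depend on it. The change should be made because it is cheap and improves safety capture, but the trial's main result does not turn on it.

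**What to change.** In 6.6, delete the hazard condition from the lead-in, from *suggests* up to and including the *and* that joins it to the outcome criteria. Define an SAE as any untoward medical event that meets at least one listed criterion, regardless of suspected cause. Keep the closing paragraph, so that the investigator can still add medically important events. Sections 6.5 and 6.7 then handle relatedness as they already do, and 6.2 needs no change for this purpose.

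At most, add one sentence to 4.1 stating that adverse-event incidence and withdrawals due to adverse events refer to the events collected under 6.2 plus SAEs.

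The cost is a wording amendment and somewhat more SAE forms for unrelated events. Admissions within 12 months are already counted, so the added work there is mainly the form and narrative.
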